# 5.13. Subject Registry Completion

A subject has completed the registry when the all expected follow-up visits have been completed and properly recorded in the EDC. Any subject who does not complete these requirements due to voluntary withdrawal, physician withdrawal, death, or any other reason will be considered a withdrawal.

### 5.13.1. Subject Discontinuation

Subjects will be discontinued from the registry in case of the explant of the device or renal transplantation for subjects enrolled in the AV access cohort.

### 5.14. Explant Procedures

Not applicable due to the retrospective data collection.

# 6. Registry Administration

### 6.1. Training

All Investigators involved in this registry must be trained on the protocol, EDC and Good Document Practice by Sponsor associates, designees, or another appropriately trained physician at the registry Site.

### 6.2. Monitoring

Site monitoring for this protocol will be provided by Contract Research Organization (CRO). Monitoring oversight will be provided by the sponsor.

The site monitors are qualified by training and experience to oversee the progress of the registry at the site and will verify that the investigators and their staff understand and adhere to both the applicable regulatory requirements and the protocol. In addition, they may assist in resolution of any problems that may arise during the registry.

### 6.2.1. Site Initiation

The start of this registry corresponds with the first site initiation perform at the first site. Site initiation will be performed to verify that each investigator and his / her staff understands the protocol, applicable regulations, human subject protection requirements, and the investigator's obligations. This visit will confirm that required documentation with the appropriate approval is in place prior to subject enrollment.

Doc Type: GC

The clinical investigation shall not begin until the sponsor has confirmed the required approval / favorable opinion from the EC or regulatory authority have been obtained. Site Initiation can be performed remotely (web-conference) if onsite visit is not possible.

#### 6.2.2. Periodic Site Monitoring

Periodic site monitoring will occur as necessary to verify continuing adequacy of facilities and adherence to the protocol, Good Clinical Practices (GCPs), and applicable regulations and laws that pertain to the conduct of the registry. These activities will also review the Case Report Forms (CRFs) and source documentation, the timely submission of accurate records to the sponsor, and the maintenance of proper records. A report will be written following each site visit and a follow-up letter will be provided to the site with a summary of findings. Each site will also be visited at close-out to confirm that all documentation is complete.

The registry will employ a risk-based monitoring approach where data are reviewed remotely and centrally for logical context, completeness, and obvious outliers. Only specific critical data variables will be source verified during on-site visits. Informed consent documentation for all patients will be reviewed to verify that all patients agreed to registry participation. Monitoring procedures and requirements will be documented in a clinical monitoring plan developed and maintained by Gore.

## 6.3. Device Accountability and Storage

Due to the retrospective nature of this registry, participating sites will have utilized their commercial contractual agreement with the Sponsor or designee for device shipping, storage, use and return. Implanted device part numbers will be collected on CRFs, if available.

#### 6.4. Core Lab

Not applicable. This registry will not utilize a Core Lab for evaluation of imaging.

# 6.5. Protocol Deviations

The investigator must follow the protocol, except in the event of an immediate hazard(s) to a subject. The investigator must report those deviations immediately to the sponsor. The investigator will report the protocol deviation in accordance with the applicable regulations.

A protocol deviation is defined as any change, divergence, or departure from the registry design or procedures of a research protocol. The investigator is responsible for promptly recording and reporting protocol deviations to the sponsor and the reviewing Ethic Committee (EC) per EC policy. The sponsor will determine the effect of the protocol deviation on the scientific soundness of the registry and subject safety and determine if additional reports or actions are required. Additional action may include site retraining, removal of devices from the site, and / or site termination.

The investigator will not implement any changes to the protocol without first obtaining written agreement from the sponsor and documented approval from the EC, except in the event of an immediate hazard(s) to a subject. The investigator will document and report the protocol deviation in accordance with the applicable regulations. Protocol deviations will be analyzed by the sponsor and reported to regulatory authorities in accordance with applicable regulations.

Considering the retrospective nature of this registry, protocol deviations would only affect the informed consent signature process and verification of inclusion / exclusion criteria.

#### 6.6. Protocol Amendments

The protocol may be amended by the sponsor throughout the life of the registry, as result of new findings or advisement from the applicable regulatory body or advisory committee. The investigator will obtain EC approval on all amendments in a timely manner. The sponsor will confirm proper training of Investigator and site staff on all protocol amendments.

#### 6.7. Access to Source Data / Documents

Source data are defined as all information necessary for the reconstruction and evaluation of the clinical investigation.

The investigator should maintain adequate and accurate source documents and registry records that include all pertinent observations on each registry subject. Source data should be attributable, legible, contemporaneous, original, accurate, and complete. Changes to source data should be traceable, should not obscure the original entry and should be explained if necessary (e.g., via an audit trail).

Where copies of the original source documents or printouts are retained, these need to be signed and dated by a member of the study team with a statement that it is a true reproduction of the original source.

The investigator will keep all study records, source data, and investigational devices available for inspection by the sponsor, sponsor's monitors, EC, and regulatory authorities.

### 6.8. Registry Records Retention

The investigator will maintain complete, accurate, and current registry records as required by applicable regulatory requirements. Records will be maintained during the registry and for a minimum of fifteen years after the latter of the date on which the registry is terminated or completed. In any event, registry records will not be disposed of, nor custody of the records transferred, without prior written sponsor approval.

Investigator records will include, but not be limited to:

- All correspondence with another investigator, an EC, the sponsor, a monitor, or regulatory authority, including required reports.
- Records of each subject's case history and exposure to the device. Case histories
  include the case report forms and supporting data including, for example, signed and
  dated consent forms and medical records, including, for example, progress notes of
  the physician, the individual's hospital chart(s), and the nurses' notes. Such records
  shall include:
  - Documents evidencing informed consent. In case the consent is waived, a brief description of the circumstances justifying the failure to obtain the informed consent. The case history for each individual shall document that informed consent was obtained or waived prior to participation in the registry.
  - All relevant observations, including records concerning adverse device effects (anticipated and unanticipated), the information and date and condition of each subject upon entering, and information about relevant previous medical history and the results of all diagnostic tests.

- A record of the exposure of each subject to the investigational device, including the date and time of each use, and any other therapy.
- The protocol, any amendments, and documentation of any deviations from the protocol, including the dates and the reasons for such deviations.
- Any other records that regulatory authority requires to be maintained by regulation or by specific requirement for a category of investigations or a particular investigation.
- A signed Investigator Agreement.
- Any other records as required by the regulatory authority, the EC, and the sponsor.

The investigator will prepare and submit the following reports:

- Protocol deviations shall be reported as described in section 6.
- Other: Any other reports as reasonably requested by the sponsor or required by regulatory authority.

### 6.9. Publication Plan

The International Committee of Medical Journal Editors (ICMJE) member journals have adopted a trials-registration policy as a condition for publication. According to ISO14155, this registry will be recorded in a public trials registry.

It is the intent of the sponsor that the multicenter results of this registry will be submitted for publications (in a peer reviewed journal). A publications committee will be established to review the multicenter results, data request, and develop a publication strategy. The timing of the multicenter publications may be dependent on regulatory submissions and approvals. Individual sites should coordinate requests for either single center or multicenter data through the publications committee.

### 6.10. Health Economics

The sponsor may use registry data to develop a better understanding of the impact that the device may have on clinical practice in order to meet anticipated business needs.

### 7. Data Collection and Submission

The validated Clinical Data Management System (CDMS) for this registry will be provided by

The sponsor keeps a separate Clinical Data

Management Plan (CDMP) describing the procedures for verification, validation, and security of the CDMS. The Clinical Data Management Plan will describe and document procedures regarding data management processes for this investigation.

Patient data will be retrospectively collected from the medical records and other source documentation already existing in patient files at the sites.

MD133246 Protocol Template

#### 7.1. Data Collection Methods

This registry will report clinical data using the web-based application. The CDMS will be the database of record for the protocol and subject to regulatory inspections and quality assurance review. All users will be trained to use the CDMS and will comply with registry specific guidelines / instructions as well as applicable regulatory requirements.

Subject data will be collected using protocol-specific case report forms (CRF). Site staff will enter data directly into the CRF for transmission to the sponsor. The sites will be notified of any significant amendments to the CRFs.

A source document is defined as original documents, data, and records (e.g., hospital records, clinical and office charts, laboratory notes, memoranda, subjects' diaries or evaluation checklists, recorded data from automated instruments, copies or transcriptions certified after verification as being accurate copies, x-rays, subject files, and records kept at the pharmacy, at the laboratories and at medico-technical departments involved in the clinical trial).

### 7.2. Data Clarification and Correction

Once entered, data will be evaluated to confirm that it is complete, consistent, and logically sound. If changes to the data in the CDMS are required, all changes, reasons for changes, and persons making the changes will be captured in the CDMS's audit trail. Sponsor will perform periodic data reviews throughout the entire registry. Procedures and documentation for regular and ongoing data review are described in the Clinical Data Management Plan.

# 7.3. CRF Completion Schedule

Entry of patient data into the EDC system cannot occur prior to the collection of the patient's informed consent to participate in the registry or after investigator documents that the informed consent can be waived.

#### 8. Risk Assessment

A complete listing of the known risks associated with

Vascular Grafts can be found in the applicable product IFUs. Investigators are advised to review the IFU document to familiarize themselves with these risks and correlate this information with the subject's presenting pathology and prior medical history.

## 8.1. Summary of Expected Benefits

are a commercially-marketed devices indicated for replacement or bypass of diseased vessels in patients suffering occlusive or aneurysmal diseases, in trauma patients requiring vascular replacement and for dialysis access. Patients suffering from a medical ailment described here who were treated with a would likely experience the benefit of restored patency/flow in the target lesion and relief from symptoms. The duration of this benefit would likely be appreciated by the patient throughout their lifetime as the permanent repair; however, the ability of the device to achieve its intended function may be affected by the subject's underlying condition or subsequent medical course. Participation in this study is not expected to provide any direct benefits to participating subjects. However, the data collected during the study will foster a better understanding of

. As the study will not require the use of any procedure and / or test and / or device different from those required by routine clinical practice for the investigated conditions, enrolled subjects will not be exposed to additional risks as compared to routine clinical practice.

#### 8.2. Risk-to-Benefit Rationale

As this is a retrospective study, there is no potential for physical risks to subjects. There is a minimal risk of breaches of confidentiality since subject information will be collected and analyzed for the proposed study. However, appropriate measures will be taken to minimize the risk as much as possible. All information entered into the central database will be de-identified. This study will abide by all regulations related to protecting human subjects and protected health information (PHI).

The study does not use any clinical procedures, tests, devices from those required by routine clinical practice, enrolled subjects will not be exposed to additional risks when compared to routine clinical practice.

# 9. Adverse Events and Safety Monitoring

# 9.1. Anticipated Adverse Events

Anticipated adverse events are medical complications that are known to be associated with PAD, artery aneurysm and dialysis access patients undergoing surgical procedure with treatment with See section 8. Risk Assessment.

#### 9.1.1. Adverse Event Relationship

Each reported AE will be assessed by the investigator for its primary suspected relationship to the device, procedure or disease.

Only one primary relationship will be assigned to each reported AE.

### **Registry Device-related**

The functioning or characteristics of the device caused or contributed to the adverse event.

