# 3.3. Registry Endpoint(s)

### 3.3.1. Definitions

Outcome	Definition
Primary Patency	
Aortic Aneurysm / PAD Cohort	Patency of the study graft without additional or secondary surgical or endovascular procedures to maintain or restore flow to the graft. The only exceptions that do not disqualify the graft for primary patency are procedures performed for disease beyond the graft and its two anastomoses.
Dialysis Access Cohort	Interval following intervention until the next access thrombosis or repeated intervention.
Secondary Patency	
Aortic Aneurysm / PAD Cohort	Patency of the study graft with additional or secondary surgical or endovascular procedures to restore flow to the graft after occlusion or stenosis of the graft or its anastomoses  The only exceptions that do not disqualify the graft for secondary patency are procedures performed for disease beyond the graft and its two anastomoses
Dialysis Access Cohort	Patency of the study graft from the time of access creation or placement until access abandonment
Limb Salvage	Freedom from an amputation above the level of the ankle of the index limb
Amputation Free survival	Freedom from an amputation above the level of the ankle of the index limb or all cause death
Device-related seroma or infection PAD Cohort	Clinical evidence of an infectious process in the direct vicinity of the access site or distal to the treated vascular site or seroma classified by the registry investigator as primarily related to the registry device

Device-related infection requiring reoperation PAD Cohort	Clinical evidence of an infectious process in the direct vicinity of the access site or distal to the treated vascular site classified by the registry investigator as primarily related to the registry device and required surgical intervention
Device-related infection  Dialysis Access Cohort	Clinical evidence of an infectious process in the direct vicinity of the access site classified by the study investigator as primarily related to the study device
Survival	All Cause survival
Device-related Adverse Events	Any untoward medical occurrence classified by the registry investigator as primarily related to the registry device

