### **Registry Procedure-related**

The registry procedure (and not the device or other adjunctive procedure) caused or significantly contributed to the adverse event.

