#### **Registry Disease-related**

The adverse event was a result of the underlying disease progression for which the registry procedure is being performed, and not the device or procedure. Within the dialysis cohort, adverse events attributed to a cannulation procedure should be classified as registry disease-related.

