## **Unknown relationship**

The relationship of the adverse event to the device, procedure, or disease cannot be determined.

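### The endpoint wording and Protocol section 9 can be read as different tests for a device-related event, and infections or seromas of unknown relationship have no stated place in the safety outcomes

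*Protocol*

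**What the plan says.** Protocol section 9.1.1 sets the coding task: "Each reported AE will be assessed by the investigator for its primary suspected relationship to the device, procedure or disease". It adds: "Only one primary relationship will be assigned to each reported AE".

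The categories that follow are:

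- **Device-related:** "The functioning or characteristics of the device caused or contributed to the adverse event".
- **Procedure-related:** "The registry procedure (and not the device or other adjunctive procedure) caused or significantly contributed to the adverse event".
- **Disease-related:** the result of progression of the disease "for which the registry procedure is being performed, and not the device or procedure". In the dialysis cohort, events attributed to cannulation are also assigned here.
- **Not related.**
- **Unknown:** "The relationship of the adverse event to the device, procedure, or disease cannot be determined".

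Protocol 3.3.1, repeated in SAP Table 1, defines the PAD primary safety outcome as an infection at specified sites, or a "seroma classified by the registry investigator as primarily related to the registry device". The same attribution test is used for PAD infection requiring reoperation, for the dialysis primary safety outcome (which refers to the study investigator and study device) and for device-related adverse events.

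SAP 4.1 provides no clinical event committee. Protocol 10.3 and SAP 2.7 treat a subject whose primary outcome cannot be determined as missing, and SAP 5.0 leaves such subjects out of the primary analysis. In SAP 8.1, every Kaplan-Meier output for infection or seroma is restricted to device-related events.

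**The concern.** A graft infection or perigraft seroma after bypass surgery often has more than one plausible contributor, the operation and the prosthesis among them. If one rule asks whether the device contributed at all and another asks whether it was the main cause, two sites can code identical events differently, and only one coding reaches the primary safety outcome. The coding is done by the site investigator from existing chart entries, on procedures performed at least 5 years (PAD) or 2 years (dialysis) before site initiation. Unknown is therefore a realistic code, and nobody independent reviews the choice.

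The registry's stated aim is to confirm safety. If the numerator of a primary safety outcome depends on how blame is divided between graft and operation, the reported rate is hard to interpret or to set beside other series. SAP 8.1 offers no cumulative estimate that is free of that judgement.

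**Working it through.** **Step 1. A mixed-cause event under each reading.** Take a PAD graft infection to which both the operation and the prosthesis contributed.

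| Rule applied | Code | Counted? |
|---|---|---|
| Section 9 category definitions, read literally | Device-related, because a contribution is enough and the procedure and disease categories both exclude device involvement | Yes |
| One primary relationship, read as predominant cause, with the endpoint's word primarily | Procedure-related, if the investigator judges the operation the larger cause | No |

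Neither document says which reading prevails. A main-cause test is narrower than a contribution test, so where the two diverge the endpoint count can only be lower under the main-cause reading.

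**Step 2. An event coded unknown.** It has not been classified as primarily device-related, so it is not an endpoint event. Let *n* be the subjects, *e* those with an infection or seroma, and *u* those of the *e* whose only such event is coded unknown. Suppose all the others are coded device-related.

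- Counted as non-events: reported rate = (*e* − *u*)/*n*, which is below *e*/*n*.
- Treated as missing: reported rate = (*e* − *u*)/(*n* − *u*). This is below *e*/*n* whenever *n*(*e* − *u*) < *e*(*n* − *u*), that is, whenever *e* < *n*.

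So both treatments give a figure below the proportion of subjects who had an infection or seroma. Excluding them also removes subjects known to have had one.

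**Step 3. The plan's own figure.** SAP 2.6 and Table 2 give 72 PAD patients per device, for an exact 95% half-width of 12% at about 55%. The Clopper-Pearson half-width for *n* = 72 is 11.97% at 55% and 11.94% at 56%, so the figure reproduces. It was set on secondary patency. No infection or seroma rate is assumed in either document, so the present point does not alter the sample size.

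**Step 4. Illustration with assumed counts.** The 9 events and the recoded shares below are assumptions. Intervals are exact 95%.

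| Coding of 9 infections or seromas in 72 subjects | Reported | 95% CI |
|---|---|---|
| All counted | 9/72 = 12.5% | 5.9% to 22.4% |
| 3 coded otherwise, kept as non-events | 6/72 = 8.3% | 3.1% to 17.3% |
| 3 coded unknown, dropped as missing | 6/69 = 8.7% | 3.3% to 18.0% |
| 6 coded otherwise, kept as non-events | 3/72 = 4.2% | 0.9% to 11.7% |

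At this cohort size, a few coding decisions visibly move the estimate.

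**Step 5. What other outputs show.** SAP 8.1 plans tables of all adverse events and all serious adverse events by MedDRA term and follow-up interval, and a table of device- or procedure-related serious events. SAP 8.2 lists all adverse events. Events lost from the endpoint would therefore still appear. They would appear as counts by term and interval, without a cumulative estimate and confidence interval at 5 or 2 years. The device-or-procedure table also leaves out non-serious events and those of unknown relationship.

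**The case against.** The strongest reply is that section 9 is coherent as written. The single relationship in 9.1.1 is chosen from categories whose definitions follow directly. The procedure and disease categories both exclude device involvement, and the endpoint's word primarily can simply refer to that one code. A mixed-cause event is then device-related and is counted. The device test is also the wider one, since it asks for a contribution where the procedure test asks for a significant one.

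This reply stands in large part. A reader might infer that events to which the device contributed necessarily drop out of the safety outcome. The documents do not support that: on their literal definitions such events count, and loss arises only if an investigator applies a predominant-cause reading. The reply does not remove the ambiguity, because no text gives the category definitions precedence over the instruction to pick one primary relationship.

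A reader might also infer that every ambiguous event becomes a non-event with the subject kept in the denominator. That is not stated either. The missing-outcome rule could apply to events of unknown relationship and shrink the denominator.

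Finally, the study is descriptive, with no hypothesis test, and the adverse event tables keep the events visible. That limits the consequence, but it does not supply the missing cumulative estimate.

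**Conclusion.** The point holds as an ambiguity in the coding rule and a gap in the handling of unknown events. It does not establish a certain loss of device-contributed events. Two parts are firm: infections and seromas of unknown relationship are not endpoint events, and every planned cumulative infection or seroma estimate rests on one unadjudicated retrospective attribution. Undercounting of mixed-cause events is possible, depending on how sites read 9.1.1.

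The outcomes affected are the PAD and dialysis primary safety outcomes, PAD infection requiring reoperation, and the 1-year device-related adverse event outcomes in both cohorts. The size cannot be derived, because the documents give neither an infection rate nor a split by relationship; the illustrative figures rest wholly on assumed counts. The change is worth making because it is cheap and bears on primary safety outcomes.

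**What to change.** 1. In Protocol 3.3.1 and 9.1.1 and SAP Table 1, state that any contribution by the device is coded device-related and counts as an endpoint event.
2. In the same places, state that a subject with an infection or seroma of unknown relationship is not dropped as missing. That subject stays in the denominator of the device-related estimate and counts as an event in the estimate under item 3.
3. In SAP 8.1, beside each device-related infection or seroma estimate (PAD at 5 years, including infection requiring reoperation; dialysis at 2 years), add the same estimate with its 95% confidence interval for all events meeting the clinical part of the Table 1 definition, whatever the recorded relationship. Include procedure-related, disease-related and unknown events. In dialysis this will take in infections attributed to cannulation, so it should sit beside the device-related figure and not replace it.

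Protocol 9.1.3 already collects the event name, onset date and relationship, so no new data items appear to be needed. Keeping the clinical part of the existing definition avoids a new case definition. The cost is the revised wording, one extra table per outcome, and a safety figure that may look less favourable.
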